5.2 EXCLUSION CRITERIA

Any subject meeting any of the exclusion criteria will be excluded from study participation:

1. Being pregnant or nursing.
2. With autoimmune disease other than diabetes, e.g. lupus erythematosus, multiple sclerosis.
3. With current malignancy or hypo-immunity.
4. With history of recurrent cancer, metastatic cancer, cancer which has high probability of metastasis, or cancer on the limb where the study wound is located.
5. With any serum chemistry or hematology abnormalities below
 - a. AST or ALT > 5 × ULN
 - b. Serum albumin < 2.0 g/dL
 - c. Serum creatinine concentration is > 2.5 mg/dL
 - d. WBC is < 2,000/µL
 - e. ANC is < 1,000/µL
 - f. Platelet count is < 100,000/µL
6. With history of HIV infection
7. With history of alcoholism or drug abuse.
8. Received any cell-based product at the study wound.
9. Received an investigational drug, device or biological/bioactive treatment within 30 days prior to Screening Visit.
10. With any clinical condition or significant concurrent disease judged by the investigator to complicate the evaluation of the trial treatment.
11. With history of sensitivity to materials of bovine, porcine origin, or human serum albumin.
12. With active infection or active osteomyelitis in the study wound.

5.3 SCREEN FAILURES

Screen failures are defined as subjects who consent to participate in this trial but do not meet all the criteria for participation in this trial. A minimal set of screen failure information is required to ensure transparent reporting of screen failure subjects, to meet the regulatory authority requirement and to respond to queries from regulatory authorities and IRBs/IECs. Minimal information includes demography, screen failure details, and any serious adverse event.

Re-screening for subject's eligibility will be allowed if the subject is willing to participate in the study and one of the following conditions meets:

1. If a subject consents to participate and meets the eligibility criteria but a delay occurs in starting the participation and that some measurement relevant to eligibility became invalid owing to the delay.

2. If the cause of screen failure has now resolved or adequately treated with medication, and the subject condition has now stabilized.
3. If there is an alternative manner to indicate that the subject may be suitable.

In these situations,

1. A new CRF will be used
2. A new screening number will be assigned to the person
3. The person will be marked as having been re-screened on the source document
4. The old CRF will be completed as fully as possible and data on the old CRF is not copied to the new CRF.
5. The subject needs to sign a new ICF as part of the screening procedure.

It is not appropriate to re-screen a subject if he/she has previously failed to meet the eligibility criteria and no further changes or treatments have been able to indicate that the subject may be suitable.

6 STUDY INTERVENTION

6.1 STUDY INTERVENTION(S) ADMINISTRATION

6.1.1 STUDY INTERVENTION DESCRIPTION

TWB-103 is a mixture of TWB-102 Cell and TWB-103 Hydrogel. TWB-102 Cell is a frozen vial containing 0.4 mL of 3×10^6 human fetal dermal fibroblasts and TWB-103 Hydrogel is a refrigerated glass vial containing 6 mL of gelatin-based hydrogel. To prepare for clinical application, TWB-102 Cell vial will be warmed to thaw and TWB-103 Hydrogel will be warmed to liquefy. Then cells from one vial will be mixed with 4.6 mL of hydrogel in a syringe to result in a 5 mL mixture containing 6×10^5 cells/mL. If less than 1 mL of TWB-103 will be applied, the mixture will further be transferred to a 1 mL syringe before it starts to thicken.

6.1.2 DOSING AND ADMINISTRATION

Dosing

Each subject will receive TWB-103 weekly up to 12 applications or till confirmed wound closure, whichever comes first. TWB-103 is applied to the ulcer at appropriate amount based on the ulcer area. The dosage of TWB-103 used in this study is 0.15 ml TWB-103/cm² of ulcer area. Detailed protocol of preparing TWB-103 for clinical application will be provided by study sponsor.

Before Administration

- (1) Before TWB-103 Treatment starts, the wound dressing and topical drugs used during screen period should be removed first. Attention should be paid to viscous substances such as gel or ointment and anti-microbial substances because they may interfere with the subsequent TWB-103 treatment by conferring physical barrier or cytotoxicity to cells in TWB-103. If such substance has been applied previously, the substance should be thoroughly washed off by flushing with sterile saline or wiping off with saline-saturated cotton swabs.
- (2) Wound debridement may be performed based on Investigator's judgment. Epinephrine is allowed for reducing bleed.
- (3) When bleeding stops, an OPSITE™ transparent film is placed on the wound and the wound area is traced on the film. The area of the wound is estimated using the grid pattern on the film. The investigator is allowed to perform additional wound measurement with a 3D camera combined with software which is capable of estimation of wound dimensions.

(4) Surgical removal of excessive granulation tissue and minor wound debridement are allowed during study period. However, such events should be recorded and photo images before and after the procedure should be taken.

Administration

- (1) TWB-103 is pushed from the syringe to the wound. The wound is then covered by Tegaderm™ transparent film. If the wound is positioned in a way that TWB-103 might flow-off easily, a collagen wound dressing (provided by Sponsor) can be placed within the wound after TWB-103 administration and before covering the wound with the Tegaderm™ transparent film. It is appropriate that the collagen dressing loosely fills the wound after it is applied. Prewetting of the collagen dressing is not suggested since TWB-103 contains sufficient liquid.
- (2) Then, gauze pad, additional dressings, fixation bandages or sleeves, etc. may be applied over the wound for further protection.
- (3) Gauze pad and dressing on top of Tegaderm™ transparent film should be replaced as frequently as needed for good wound care.

Note: For consistency, only one type of collagen dressings may be used for each patient. "One type of dressings" means the dressings under the same medical device approval number by Taiwan Ministry of Health and Welfare which normally covers products with various dimensions. The suitable collagen dressings are those which have no obvious cytotoxicity and do not physically obstruct the subsequent weekly administration of TWB-103 (the bulk of the dressing can be gently removed with saline rinse). The collagen dressings are of bovine or porcine origin since only patients non-allergic to bovine or porcine materials are included in this study.

Self-Care by Patient between Hospital Visits

Between applications of TWB-103 in hospital, if the transparent film becomes loose or displaced, fluid strike-through occurs or the area adhered by the film becomes itchy, the following management is applied:

- (1) The gauze, dressing and Tegaderm™ transparent film are removed.
- (2) The wound is gently cleaned with gauze moisturized with normal saline, then pat-dried with gauze. No effort is required to remove the residual TWB-103 (or the collagen dressing, if it is present) on wound bed.
- (3) The wound is applied with appropriate wound dressing following instruction of the investigator (see below). No additional TWB-103 is reapplied until next scheduled application.
- (4) Investigator provides instruction for appropriate dressing and sufficient amount of dressing to be applied by the subject at home based on the following principles:

- The dressing maintains the wound at moist condition, e.g. using Mepilex® or Mepilex® Border for high exudates wounds and using Mepilex® Border Lite or Mepilex® Lite for low-medium exudate wounds.
- The dressing is retained on wound by ways that will not cause itchiness or irritation to the subject, e.g. by adhesives well tolerable to the subject, by elasticated bandages, such as Tubifast®.
- The dressing should not stick to the wound bed, to avoid damaging the newly formed tissue.
- The dressing should be able to be removed completely with easiness, to avoid interfering with subsequent TWB-103 treatment.

(5) In principle, dressings with anti-microbial activity should not be used for study wounds during TWB-103 treatment period unless approved by sponsor after consultation. Sponsor's approval will be based on the confirmation that the anti-microbial activity of the dressing is not toxic to human dermal fibroblast or keratinocyte. Likewise, the use of topical treatment for infection should also have sponsor's approval. However, systemic treatments (oral administration) to control infection (\leq Grade 2) are allowed.

6.2 PREPARATION/HANDLING/STORAGE/ACCOUNTABILITY

6.2.1 ACQUISITION AND ACCOUNTABILITY

The sponsor is responsible for supplying the investigator(s)/study site(s) with the investigational products (IP). The IP must not be used for the purposes other than this trial, and the clinical trial pharmacist or designated qualified personnel must record the quantity of IP supplied/returned by/to the sponsor to maintain clear drug inventory control. Acquisition of IP from pharmacy for clinical administration as well as the amount of IP applied to each wound should also be recorded.

[figure not shown]
The investigator or designated qualified personnel must retain all unused and leftover IP until the study monitor has confirmed accountability data and the sponsor has given instruction for the final handle of the IP. Any discrepancy noted will be investigated, resolved, and documented prior to returning or destruction of unused study drug. Leftover or unused IP should be returned to the sponsor for destruction or be destroyed at the study site according to standard institutional procedures after drug accountability has been conducted by the sponsor or representative.

6.2.2 FORMULATION, APPEARANCE, PACKAGING, AND LABELING

TWB-103 used in this study will be prepared, packaged, and labeled under the responsibility of a qualified person at sponsor with Standard Operating Procedures (SOPs) of sponsor, Good Tissue Practice (GTP) guidelines, International Conference on Harmonization Good Clinical Practice (ICH GCP)

guidelines, and applicable local laws/regulations. TWB-102 Cell is supplied in a frozen plastic vial, with the secondary package of aluminum pouch. TWB-103 Hydrogel is supplied in a refrigerated glass vial, with the secondary package of aluminum pouch. The product will be labeled with descriptions of “Clinical trial use only” as well as other required information in the local language according to the regulatory requirements.

The Figure below shows the representative appearance of IP in primary and secondary packages.

Primary package of TWB-102 Cell	TWB-102 Cell vial in aluminum pouch
	
Primary package of TWB-103 hydrogel	TWB-103 hydrogel vial in aluminum pouch
	

6.2.3 PRODUCT STORAGE AND STABILITY

Once packaged and stored at -70 ~ -80°C, TWB-102 Cell has at least 6 months of shelf-life. TWB-102 cell vials should be directly transferred from dry ice (shipping condition) to a freezer which has been validated for maintaining temperature not higher than -70°C. If no suitable freezer is available, a well-insulated container loaded with dry ice can be used. In such case, the TWB-102 cell vial should be fully buried within dry ice until use.

Stored at 2~6°C, the TWB-103 Hydrogel has 12 months of shelf life after manufacturing. TWB-103 hydrogel vials should be stored in a validated 4°C refrigerator. The hydrogel is in gel-form at cold temperature and the vials can be stored in standing or lying position.

The two components of TWB-103 are stored separately but will be used together by the bedside.

6.2.4 PREPERATION

TWB-103 should be prepared by mixing a vial of TWB-102 cells (0.4 mL) with 4.6 mL of hydrogel in a 5 mL syringe and let the mixture cool to thicken enough for the convenience of applying it to wound. A water-bath set at 37°C is required for the procedure. Briefly, a hydrogel vial is removed from the aluminum pouch and put in a water bath to be warmed to liquefy. When hydrogel is fully liquefied (taking about 20 min), a cell product in aluminum pouch is removed from the ultra cold storage (deep freezer or dry ice), then the cell vial is immediately removed from the pouch and put in the water bath for quick thaw. It usually takes about 80 seconds to thaw the cells. After thaw, the cell solution from one vial is drawn into a 5 mL-syringe through an 18-G needle, and then 4.6 mL of hydrogel is drawn into the same syringe. The hydrogel and cells are thoroughly mixed in the syringe. If less than one mL of TWB-103 will be applied to the wound, the mixture is transferred to 1 mL- syringe through a syringe connector. The syringe is then set aside at room temperature until it thickens and convenient to be applied onto the wound. If the wound is deep and there is no concern for the IP run-off from wound, the IP need not thicken before applied to the wound.

After the cell vial is thawed, the cells should be soon mixed with hydrogel. The maximum time between cell-thaw and mixing with hydrogel is 30 minutes. The prepared TWB-103 (i.e. mixture of thawed cells and hydrogel) is stable at room temperature (or up to 37°C) for at least 2 hours, providing adequate flexibility of preparation time for the study staff.

6.3 MEASURES TO MINIMIZE BIAS: RANDOMIZATION AND BLINDING

As this is an open-label study, no blinding will be used in this study.

6.4 STUDY INTERVENTION COMPLIANCE

TWB-103 will be administered at the study site at scheduled visits. Subject's compliance should not be a severe issue. However, the study monitor will assure the subject's compliance with the study protocol.

6.5 CONCOMITANT THERAPY/MEDICATION

Concomitant therapy is defined as any therapy including surgeries, vaccines, prescriptions, or over the counter medications. Subjects are allowed to receive routinely used medications or treatments for other indications which is judged by the investigator as not affecting the efficacy and safety assessments of this study. All therapies taken by the subject prior to the Screening Visit as well as throughout the study will be recorded on the appropriate page of the case report form (CRF)/electronic CRF (eCRF). Therapies will be categorized as follows:

- Major surgeries: will be recorded on a life time base
- Therapies for diabetic lower limb ulcer: will be recorded up to 2 months before Screening Visit
- All other medications: will be recorded up to 30 days before Screening Visit

This record will include the name of the therapy, frequency, unit dose, routes, dates of the drug is started and stopped (if medication/therapy is not ongoing), and the indication for the use of the drug.

6.6 PROHIBITED THERAPY/MEDICATION

Prohibited therapy or medication are defined as below:

- Any other investigational drug, device or biological/bioactive treatment during the study period.
- Any treatment/therapy applied to target wound area that may affect the efficacy evaluation of study medication at the investigator's discretion, such as revascularization, hyperbaric oxygen therapy, negative-pressure wound therapy, during TWB-103 treatment period.
- Dressings with anti-microbial activity should not be used for study wounds during TWB-103 treatment period unless approved by sponsor after consultation.
- Antibiotics administered via intravenous injection or intramuscular injection during TWB-103 treatment period.

6.7 STANDARD OF CARE FOR DIABETIC LOWER LIMB ULCERS

Standard care will be documented in CRF including the type of care (e.g., extent of debridement, use of concomitant medications), timing, and frequency. Parameters for consideration in choosing standard care procedures for diabetic lower limb ulcer include, but not limited, the following:

- Debridement: Removal of necrotic or infected tissue. During TWB-103 treatment period, if judged by the investigator as appropriate, lesser wound debridement is allowed. However, if major surgery is required, the subject should be withdrawn from this study.
- Off-loading: During study period, off-loading devices, such as clutches, wheel chair, off-loading

shoes, etc., may be applied as judged by Investigator.

- Revascularization or other treatment to improve circulation. However, revascularization is prohibited during treatment period (Visit 2~Visit 13).
- Maintenance of a moist wound environment.
- Management of wound infection: If the target wound has low grade infection (\leq Grade 2) during TWB-103 treatment, whether to stop TWB-103 treatment will be judged by the investigator and appropriate treatment to control the infection will be provided at the investigator's discretion. However, if wound is infected ($>$ Grade 2) during TWB-103 treatment or the treatment for the ulcer wound infection requires subject's hospitalization, intravenous infusion or muscular injection of antibiotics, TWB-103 treatment must stop and be replaced by appropriate treatment to control the infection.
- Wound cleansing
- Good blood glucose control: Considering each subject's physical and physiological condition, "good blood glucose control" is defined as blood glucose level as good as possible with the help of physicians. Subjects will have appropriate medication and education to control the blood glucose level. The investigator will also monitor subjects' blood glucose level through the laboratory tests, including fasting glucose and HbA1c test results, collected during this study.

7 STUDY INTERVENTION DISCONTINUATION AND SUBJECT WITHDRAWAL

7.1 STUDY INTERVENTION DISCONTINUATION

If the target wound has low grade infection (\leq Grade 2) during TWB-103 treatment, TWB-103 treatment may continue or discontinue as judged by the investigator and appropriate treatment to control the infection will be provided at the investigator's discretion. However, any subject with $>$ Grade 2 skin infection in the ulcer wound, or the treatment for the ulcer wound infection requires subject's hospitalization, intravenous infusion or muscular injection of antibiotics, must not receive any further TWB-103 treatment.

If allergy is judged as likely due to the investigational product, it is dangerous to continue using the investigational product. Therefore, any subject who experiences \geq Grade 1 allergic reaction at least possibly related to the investigational product (section 8.4.3.2) must stop TWB-103 immediately.

During TWB-103 treatment period, if judged by the investigator as appropriate, lesser wound debridement is allowed. However, if major surgery is required, the subject should stop TWB-103 treatment.

7.2 SUBJECT WITHDRAWAL FROM THE STUDY

A subject may withdraw voluntarily or involuntarily from the trial due to any of the following conditions:

1. The subject voluntarily decides to withdraw her/his consent.
2. The subject's pregnancy is confirmed after enrollment till last dose of TWB-103.
3. The subject received or plans to receive any prohibited therapy as defined in section 6.6.
4. The subject dies or is lost to follow-up.
5. Any pathological event, clinical adverse event, laboratory abnormality, intercurrent illness, or any occurrence or change in the subject's status giving indication to the investigator that further participation in the study may not be the best interest of the subject.
6. The subject develops $>$ Grade 2 skin infection in the ulcer wound, or the treatment for the ulcer wound infection requires subject's hospitalization, intravenous infusion or muscular injection of antibiotics.
7. The subject experiences \geq Grade 1 allergic reaction at least possibly related to the investigational product (section 8.4.3.2).
8. The subject requires a major surgery debridement.

9. The study is terminated prematurely by the investigator, research institution, sponsor, IRB/IEC or regulatory authorities.

If the withdrawal is decided during TWB-103 treatment period, the withdrawn subject will be encouraged to complete the assessments of Week 12, within 1 week of the withdrawal decision, as End of Study (EOS) visit before exiting from the study. Laboratory, pregnancy and PRA tests done within 1 week prior to EOS visit are acceptable.

If the withdrawal is decided in the follow-up period, the withdrawn subject will be encouraged to complete the assessments of Week 36, within 2 weeks of the withdrawal decision, as EOS visit before exiting from the study.

The reason for withdrawal must be recorded. If a subject is withdrawn due to an AE, every effort will be made to follow the event until event resolves or stabilizes at a level acceptable to the investigator.

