The first 3 subjects will be recruited sequentially with a 3-week staggering in the initiation of study treatment. Any subject who experiences \geq Grade 1 allergic reaction at least possibly related to the investigational product (section 8.4.3.2), has $>$ Grade 2 skin infection in the ulcer wound, or the treatment for the ulcer wound infection requires subject's hospitalization, intravenous infusion or muscular injection

of antibiotics, must not receive any further TWB-103 treatment. Additionally, if major surgery debridement is required, the subject should stop TWB-103 treatment. The study will be stopped when ≥ 3 subjects received TWB-103 have developed grade 3 or above AEs according to CTCAE 5.0, independent of attribution. If the cause of AE can be identified and resolved, the study may be resumed.

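### Major surgery means leaving the study in 6.7 but only stopping TWB-103 in 4.1 and 7.1, and 7.2 permits exit after infection or allergy, so up to 24 weeks of required safety follow-up can be lost

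*Combined protocol and SAP*

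**What the plan says.** Major surgery during treatment has three stated consequences in the protocol:

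- Section 6.7: "if major surgery is required, the subject should be withdrawn from this study".
- Section 7.1: "if major surgery is required, the subject should stop TWB-103 treatment". Section 4.1 agrees: "if major surgery debridement is required, the subject should stop TWB-103 treatment".
- Section 7.2 item 8 lists major surgical debridement under the permissive opening "A subject may withdraw voluntarily or involuntarily from the trial due to any of the following conditions".

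For wound infection above Grade 2, or infection needing admission or injected antibiotics, and for possibly related allergic reactions, 4.1 and 7.1 stop TWB-103 and say nothing about leaving the trial. Items 6 and 7 of 7.2 list the same events as grounds for leaving. Item 3 adds a further route: "The subject received or plans to receive any prohibited therapy as defined in section 6.6". Section 6.6 includes among the prohibited therapies "Antibiotics administered via intravenous injection or intramuscular injection during TWB-103 treatment period".

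After a withdrawal decided during treatment, "the withdrawn subject will be encouraged to complete the assessments of Week 12, within 1 week of the withdrawal decision", and the subject then exits. Section 4.4 treats that visit as completion of the study for such a subject. Section 4.2 gives long-term safety as a reason why the 24-week follow-up is required.

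Section 9.3 runs the safety analysis on the ITT population, which requires at least one application and also some evaluation after treatment.

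**The concern.** The primary objective is safety and the primary endpoint is AE and SAE incidence. The protocol singles out infection, osteomyelitis, cellulitis and unexpected surgery for specific discussion. The events that can end a subject's observation are therefore largely primary-endpoint events, and the subjects concerned are plausibly those in whom further events matter most. Loss of follow-up on these grounds would be informative.

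Two sites could also follow the protocol faithfully and handle the same patient differently: one withdraws after major surgery under 6.7, the other stops TWB-103 under 7.1 and continues to observe. Because 4.4 counts an exit with the one visit done as a completion, the disposition figures could hide the difference. With 10 subjects, one such case is visible in every reported proportion.

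**Working it through.** The plan states no figure on this point, so there is none to reproduce. The check compares the sections and then sizes the loss.

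**1. What each trigger leads to**

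| Trigger during treatment | 4.1 and 7.1 | 6.7 | 7.2 |
|---|---|---|---|
| Major surgery | stop TWB-103 | should leave the study | may leave (item 8) |
| Infection above Grade 2, or needing admission or injected antibiotics | stop TWB-103 | stop TWB-103 and treat | may leave (item 6) |
| Injected antibiotics as prohibited therapy (6.6) | not addressed as such | not addressed as such | may leave (item 3) |
| Possibly related allergy, Grade 1 or above | stop TWB-103 | not addressed | may leave (item 7) |

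For infection, 6.7 itself says "TWB-103 treatment must stop and be replaced by appropriate treatment to control the infection". The treatment it calls for can be the injected antibiotics that item 3 makes a ground for exit.

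**2. What is still captured after exit.** Section 7.2 follows the AE that caused withdrawal, 8.4.4 follows persisting AEs, and 8.4.5 reports any SAE of which the investigator becomes aware. None of these is a procedure for finding a new event.

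**3. What a subject who stops and stays receives.** Section 4.1, schedule footnote 3, 8.3.4 and 8.3.5 give the visits timed from End-of-Treatment to early confirmed closure. Section 4.1 gives the Weeks 13 to 36 visits to those who complete the 12-week treatment period. A subject who stops for safety is not clearly assigned to either.

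**4. Follow-up at stake.** Inputs are the visit days in 1.3 and 8.3.5 and the 10 subjects in 9.2.

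- Full treatment: Day 253 − Day 85 = 168 days; 168 / 7 = 24 weeks.
- Early closure: the last visit is 168 days after End-of-Treatment, again 24 weeks.
- Planned post-treatment observation: 10 × 24 = 240 subject-weeks.
- One exit during treatment with no later visits: 24 / 240 = 10%. Two exits: 48 / 240 = 20%.
- With the existing visits restored: 0 of the 24 weeks lost.

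**5. Effect on the endpoint.** One subject is 1 / 10 = 10 percentage points. As an illustration, suppose an exited subject with a non-serious trigger later has the study's only SAE and it goes undetected. The report is then 0/10 (exact 95% CI 0 to 30.8%) instead of 1/10 (0.3 to 44.5%). If the trigger was itself an SAE, SAE incidence does not change.

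**6. Safety set.** Under 9.3, a dosed subject who dies or is lost before any evaluation can drop out. Removing one event-free subject moves 3/10 = 30.0% to 3/9 = 33.3%. If the excluded subject had the only event, 1/10 becomes 0/9 (exact 95% CI 0 to 33.6%).

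**The case against.** The strongest reply is that exit during treatment is a defined design choice. Section 4.4 names a completion point for it, 7.2 says only that a subject may leave, and 6.7 differs from 7.2 item 8 only in force. Section 7.1 concerns dosing and does not promise that the subject stays. A reader might infer that 6.7 and 7.1 are logically opposed. They are not, because withdrawing a subject also stops TWB-103. What stands is an inconsistency over whether observation continues, and it falls on the primary endpoint.

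Second, much of the endpoint is protected. An infection or allergy trigger is already an AE, so overall AE incidence is unchanged by exit. An infection above Grade 2 already counts toward the stopping rule of three subjects with Grade 3+ events, and admission already makes the event an SAE. This stands and narrows the point to low-grade allergy, infection graded 2 or lower but treated by injection, or non-serious surgery, followed by a new and worse event.

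Third, the missing schedule can be read away: Weeks 13 to 36 run from Day 1, and a subject off TWB-103 might still be said to complete the 12-week period. That reading is available but not stated.

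Fourth, the 9.3 exclusion is unlikely, since an AE assessment after dosing might count as an evaluation. That is fair, but the condition serves no purpose in a safety set. Section 9.4.1 leaves population detail to a later SAP, yet 9.3 already sets the rule.

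**Conclusion.** The inconsistency is real and worth correcting. As written, 6.7 removes a subject needing major surgery from follow-up, and 7.2 allows the same after infection, allergy or injected antibiotics. Each exit during treatment loses up to 24 weeks of planned post-treatment observation, which is 10% of the 240 subject-weeks planned. Each subject is 10 percentage points of any incidence. This assumes no visits after the one encouraged visit. The loss is limited to new later events that no one reports, chiefly a first SAE or Grade 3+ event after a milder trigger.

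Two stronger readings are tempting. One measures the loss to Week 36 for everyone, so that an early stop appears to lose well over 24 weeks. The documents do not support this: the protocol's standard is 24 weeks after End-of-Treatment, and subjects with early closure are not followed to Week 36. The other attaches a probability to the problem. The documents give no rate of safety stops, and the chance of a stop would in any case not be the chance of an exit or of a missed event.

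**What to change.** (a) **Withdrawal and follow-up.**

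- In 6.7, replace study withdrawal after major surgery with a TWB-103 stop, as in 4.1 and 7.1.
- In 7.2 items 6 to 8, and in item 3 where the prohibited therapy treats a safety event, state that the event ends TWB-103 only.
- In 4.1, schedule footnote 3, 8.3.4 and 8.3.5, give these subjects an End-of-Treatment visit and then the existing visits at 1, 2, 4, 8, 12, 18 and 24 weeks after it.
- Keep as exceptions: withdrawn consent, death, loss to follow-up, the investigator's judgement under item 5 that taking part is not in the subject's interest, and study termination.
- Amend 4.4 so that a subject withdrawn during treatment is not counted as having completed the study.

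No AE collection beyond those 24 weeks is needed.

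(b) **Safety set.** In 9.3, analyse safety on every subject with one or more TWB-103 applications, with no condition on later evaluation.

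The cost is protocol wording and one analysis-set definition. A few stopped subjects attend up to 7 visits that already exist in the schedule. No patients or procedures are added. The rules for when TWB-103 must stop and the per-protocol definition are unchanged. Item 5 still leaves the investigator some discretion over exit, which is appropriate.
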